**Twenty (20) subjects will begin low dose tacrolimus with concentration controlled everolimus (treatment arm)**

Tacrolimus will be initiated according to our practice. In this treatment arm, the Tacrolimus dose will be adjusted from day 3 on, to a target whole blood trough concentration of 4 ng/mL to 7 ng/mL. From month 2 until Month 6, the target Tacrolimus trough level will be 3 ng/mL to 6 ng/mL. After month 6, the Tacrolimus dose should be adjusted in order to achieve a target trough level of 2 ng/mL to 5 ng/mL.

From day 5 on, the starting dose of Everolimus (0.75 mg bid) will be increased if the trough level is < 3 ng/mL, or reduced if the trough level is > 8 ng/mL.

All drugs will be administered in an open label fashion.

The following transplant recipient data will be collected at the time of randomization:.  
Demographics: Age at transplantation, sex and race.

Causes of end-stage renal disease

Transplant related information: donor age, histocompatibility and cross match data, viral serology, history of acute rejection and delayed graft function, use of ACEI and/or ARB, level of renal allograft function - estimated GFR ( e-GFR(12) using MDRD formula, proteinuria.

Blood samples will be obtained prior to randomization from all renal transplant recipients for baseline T and B cell functional activity and characterization of the cell subpopulations by flow cytometry.

-All recipients will be routinely followed at our Transplant center with post-transplant labs (SMA7, CBC, and relevant immunosuppression trough levels).

Additional blood will be collected and analyzed for the study at 3, 6, 12, 24 and 36 months post-randomization. If the final blood sample cannot be drawn at the 36 month timepoint, it may be drawn up to 50 months post-transplant. These samples will be used to investigate the impact of the two maintenance immunosuppressive regimens on subpopulation of T cells in comparison with baseline levels. Specifically,

---

we will look at regulatory T cells (Treg: Foxp3+CD4+ CD25bright+) that could have been generated via the two maintenance immunonousuppressive regimens, and correlate the generation of with their function.

RNA from peripheral blood will be also collected and stored for post-hoc analyses of T and B-cell immunoresponse gene expression via gene arrays.

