Kidney biopsy samples will be collected with standard-of-care samples at time of transplant (back table), 3 months, 12 months and at 24 months post-transplant. These will help evaluateand compare the impacts of the two maintenance immunonousuppressive regimens on allograft immunohistopathology. Gene expression profiles will also be analyzed. These samples will be processed in the principal investigator's research laboratory.

Both groups of subjects will be followed through 36-months post-randomization. In addition to monitoring renal allograft function, we will evaluate the incidence of acute rejection, subject and graft survival, incidence of hypertension (HTN), malignancies, opportunistic infections and post-transplant diabetes mellitus (DM).

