### **Stopping Rules**

Subjects developing post-transplant infections (i.e., UTI, CMV, HSV, EBV, HCV, HBV, HIV, PCP), that in the opinion of the investigator are detrimental to the subject and his/her participation in this research trial, will be stopped from participating in this study..

Patient Authorization: This study is to be conducted according to US and international standards of Good Clinical Practice (FDA Title 21 part 312 and International Conference on Harmonization guidelines), applicable government regulations and Institutional research policies and procedures.

This protocol and any amendments will be submitted to a properly constituted independent Institutional Review Board (IRB), (Northwestern University Institutional Review Board), in agreement with local legal prescriptions, for formal approval of the study conduct. The decision of the IRB concerning the conduct of the study will be made in writing to the investigator and a copy of this decision will be provided to the investigator/sponsor before commencement of this study. The investigator will place a list of IRB members and their affiliate in the regulatory binder for the clinical trial.

All subjects for this study will be provided with a printed consent form describing this study and providing sufficient information for subjects to make an informed decision

---

about their participation in this study. This consent form will be submitted with the protocol for review and approval by the IRB for the study. The formal consent of a subject, using the IRB-approved consent form, will be obtained before the subject is submitted to any study procedures. This consent form will be signed by the subject and the investigator-designated research professional obtaining the consent. The subject will be given a signed copy of the informed consent for their records.

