**Statistical analysis:**

The primary endpoints of the study are graft function and subpopulations of T cells, including regulatory T cells and B cell subpopulations at 3, 6, 12, 24 and 36 months post kidney transplant. The secondary endpoints of the study include 1) incidence of acute rejection, graft loss, and death at 12, 24 and 36 months post kidney transplant; 2) allograft immunohistopathology and gene expression profiles at 12 and 24 months post kidney transplant.

We will run univariate and bivariate analyses for all variables prior to our main analyses. We will evaluate continuous variables using t-tests or F-tests and categorical variables using  $\chi^2$ . We will examine data distributions and test all variables for linear relationships or non-linear relationships.

Descriptive statistics (means, standard deviation, frequency) and correlations (both Pearson and Spearman) among variables will be calculated for preliminary data assessment.

Necessary transformation and imputations will be carried out based on the raw data distribution.

As missing data are inevitable in a longitudinal study, we will determine whether missing data are MCAR (data are missing completely at random), MAR (data are missing at random), or NMAR (not missing at random). If missing data are MCAR or MAR, it is likely that the standard multivariate computations using PROC MI (multiple imputations) will not result in biased standard error estimates. However, if missing data are NMAR, we will use the "pattern mixture" approach to compute a weighted average of the parameters that are associated with the missing data to estimate what the data would have been.

For the primary objective, we hypothesize that subjects receiving low dose CNI with mTOR inhibitor (Everolimus) will exhibit significantly greater graft function and higher numbers of regulatory T cells as compared to the standard dose CNI+MMF group.

We will utilize both repeated-measures ANOVA and random mixed effect models to compare the trajectory change in graft function and proportion of regulatory T cells over 12, 24 and 36 months between the two experimental groups. The method of estimation will be maximum likelihood (ML).

---

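### The missing-data method is chosen by deciding between MAR and NMAR, which the observed data cannot do; fix one primary analysis and always run the other as sensitivity

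*Combined protocol and SAP*

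**What the plan says.** All references are to the combined protocol and SAP.

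- **Statistical analysis, missing data.** The team will "determine whether missing data are MCAR (data are missing completely at random), MAR (data are missing at random), or NMAR (not missing at random"). Two branches follow. "If missing data are MCAR or MAR, it is likely that the standard multivariate computations using PROC MI (multiple imputations") will leave standard errors unbiased. "However, if missing data are NMAR, we will use the" pattern-mixture approach. The section gives no test, criterion or identifying assumption for the decision, and no sensitivity analysis.
- **Statistical analysis, primary comparison.** "We will utilize both repeated-measures ANOVA and random mixed effect models" to compare trajectories between the arms. "The method of estimation will be maximum likelihood (ML"). It does not say which of the two models is primary, or how multiple imputation relates to either.
- **Study design, treatment-arm text.** "All drugs will be administered in an open label fashion".
- **Sample size and power.** Two-sided alpha 0.05, 20 per group, 10% attrition at 12 months; power 0.82 for an effect size of 1.0 (graft function) and 0.99 for 2.0 (% regulatory T-cell change).

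**The concern.** MAR and NMAR differ only in how the unobserved values behave given the observed ones. No analysis of the observed data can tell them apart without an assumption that is itself untestable. A rule that says to establish which one holds and then pick the method therefore cannot be carried out as written. In practice, someone would choose between two analyses with the data, and possibly both results, in view and with treatment assignment known. The two branches can give different estimates from the same data.

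At stake is the credibility of a primary result near the significance threshold. A reader could not tell whether the method was chosen for its assumptions or for its answer.

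**Working it through.** **1. Reproduce the plan's power.** Inputs from Sample size and power: two-sided alpha 0.05, 20 per arm, 10% attrition, so 20 × 0.90 = 18 evaluable per arm. Two-sample t-test, noncentral t:

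- effect 1.0: power 0.830 (stated 0.82);
- effect 2.0: power 0.9999 (stated 0.99).

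Both agree with the plan to within two points, so 18 per arm is a fair base. With 20 per arm the first figure would be 0.869, which does not match.

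**2. Can the data choose the branch?** A simulated check used one arm, 2 million subjects, two visits with correlation 0.6, and 11% missing at visit 2 by a MAR rule. The missing values were then lowered by 0, 0.5 or 1.0 SD.

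| Departure of missing values (SD) | Observed mean | Observed slope | MAR estimate | True mean |
|---|---|---|---|---|
| 0 | 0.050 | 0.600 | -0.001 | -0.001 |
| 0.5 | 0.050 | 0.600 | -0.001 | -0.057 |
| 1.0 | 0.050 | 0.600 | -0.001 | -0.113 |

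Everything observable is identical and only the truth moves. The first row is MAR and the other two are NMAR.

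Even MCAR, which can be tested, is tested weakly here. With 10% of 40 = 4 leavers against 36 stayers, a t-test on earlier values has power 0.15 for a 0.5 SD difference and 0.46 for 1.0 SD.

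**3. How far apart can the branches be?** Let k of 20 in an arm be missing, with values δ SD worse than MAR predicts. Then

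net shift = (k_E/20) × δ_E − (k_C/20) × δ_C,

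with E the everolimus arm and C control. The documents give neither k nor δ, so these values are assumed:

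- k_E = 2, δ_E = 0.5, no control departures: 2/20 × 0.5 = 0.05 SD, and an estimate of 1.0 becomes 0.95;
- k_E = 4, δ_E = 1.0, no control departures: 4/20 × 1.0 = 0.20 SD, and 1.0 becomes 0.80;
- k_E = k_C = 2, δ_E = δ_C = 1.0: 0.10 − 0.10 = 0.

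**4. Does it change the conclusion?** Smallest significant difference at 18 per arm: t(0.975, 34) × √(2/18) = 2.032 × 0.333 = 0.677 SD. Share of 1 million simulated trials that are significant before the shift and not after it, with the standard error held the same:

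| Net shift (SD) | Graft function, true effect 1.0 |
|---|---|
| 0.05 | 3.9% |
| 0.10 | 8.4% |
| 0.15 | 13.2% |
| 0.20 | 18.5% |

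For % regulatory T cells at a true effect of 2.0, all four shifts change fewer than 0.05% of trials.

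**The case against.** **The plan already names a sound method.** The maximum-likelihood mixed model is valid under MAR without imputation and needs no determination of mechanism. This stands, and it makes the repair easy. It does not rescue the rule, because the mixed model is not ranked above repeated-measures ANOVA and the switch remains in the text.

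**The illustration is one-sided.** This also stands. The 19% figure needs four everolimus leavers (all the attrition expected among 40 at 10%), none in control, and each 1 SD worse than predicted. An estimate of exactly 1.0 SD stays significant even at 0.80, above 0.68; the reversals come from trials that happen to land nearer the threshold. If control leavers did worse, the shift would run the other way.

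**The effect is close to nil for % regulatory T cells.** True at the planned 2.0 SD. The plan gives no effect size for the other cell subsets, so nothing is quantified there.

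**It is a pilot.** The plan uses pilot status to set aside power for the secondary outcomes. That does not excuse an unworkable rule for the primary ones.

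Two stronger inferences are tempting, and the documents support neither:

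- *That infection stops cut off follow-up.* Stopping Rules says of some subjects with infections: "opinion of the investigator are detrimental to the subject and his/her participation in this research trial, will be stopped from participating in this study". It does not say that data collection ends. The follow-up text says "Both groups of subjects will be followed through 36-months post-randomization", routine labs cover all recipients, and adverse events are followed up. Whether study blood sampling continues after a stop is unstated. That is a gap in detail, not a shown loss of data.
- *That replacing recipients has biased the comparison.* Population reports 3 experimental and 1 control recipients withdrawn before dosing for surgical complications. With 20 starters per arm this is 3/23 (13.0%) against 1/21 (4.8%), Fisher p = 0.61, which is compatible with chance. The target of 40 starters matches 20 per group in the design and power sections. No analysis set is named, but no bias is shown.

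**Conclusion.** The rule for choosing between multiple imputation and pattern mixture is wrong as written, because it turns on a distinction that the observed data cannot make. This follows from the definitions and does not depend on any assumed number.

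The practical size is modest and conditional. For graft function, about 4% to 19% of trials could change from significant to non-significant. That assumes a true effect of 1.0 SD, 18 per arm, an unchanged standard error, and a net shift of 0.05 to 0.20 SD from departures in one arm only. The figure is zero under balanced losses and departures, and negligible for % regulatory T cells at the planned effect. These figures are not a forecast for this trial.

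The post-stop data question and the unnamed analysis set are minor clarifications and not part of this error.

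**What to change.** In Statistical analysis:

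1. Delete the determination of mechanism and the switch that depends on it.
2. Name the maximum-likelihood mixed model as the primary analysis of the primary endpoints, stating that it assumes MAR, with repeated-measures ANOVA as supportive.
3. Always run the pattern-mixture analysis as a sensitivity analysis. Fix its departures in advance, separately by arm, and include both equal and one-sided settings. Report how large a departure would change the conclusion.

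Minor clarifications to make at the same time:

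- Reconcile Stopping Rules with the 36-month follow-up statement on whether data collection continues after an infection stop. This concerns data only and leaves treatment decisions untouched.
- Name the analysis set, and report the four recipients withdrawn before dosing by arm with reasons.

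The cost is wording in the protocol and SAP and a little more analysis work. The fix needs no extra patients and no change to randomisation, and both main methods are already in the plan.

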### **Objectives**

The overall aim of the present study is to prospectively investigate the impact of two maintenance immunosuppressive regimens (both prednisone-free) on subpopulations of T and B cells and on renal allograft function at 12, 24 and 36 months post-randomization. One regimen combines low CNI exposure (tacrolimus) with concentration controlled Everolimus, and the second combines standard dose CNI (Tacrolimus) with MMF.

The primary endpoints of the study are to: 1) evaluate the impact of the two maintenance immunosuppressive regimens on T cells subpopulations, including regulatory T cells and B cell subpopulations, at different time points post renal transplant, and 2) determine the impact of the two regimens on renal allograft function at 12, 24 and 36 months post-randomization (post-transplant). Secondary endpoints of the study are to: 1) evaluate the impact of the two regimens on allograft immunohistopathology gene expression profiles and graft infiltrating cells (memory T cell (CD4+ or CD8+ CD45RO+), TREG (CD4+FoxP3+), memory B cell (CD19+CD27+)) at 12 and 24 months in renal allograft biopsies, and 2) evaluate the impact of the regimens on acute rejection, graft loss and death at 12, 24 and 36 months post-transplant.

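### The plan does not say how eGFR after graft loss or death enters the primary analysis; under the MAR branch or the ML mixed model, lost function is predicted from working grafts

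*Combined protocol and SAP*

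**What the plan says.** The Objectives and Statistical analysis sections make graft function a primary endpoint through 36 months. The only measure named is eGFR by the MDRD formula, in the list of recipient data under Study design. The second secondary aim is to "evaluate the impact of the regimens on acute rejection, graft loss and death at 12, 24 and 36 months" after transplant. These events get their own logistic, Kaplan-Meier and Cox analyses.

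For missing data, the Statistical analysis section starts from classification: "we will determine whether missing data are MCAR (data are missing completely at random), MAR (data are missing at random), or NMAR". Two branches follow.

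- **MCAR or MAR:** "If missing data are MCAR or MAR, it is likely that the standard multivariate computations using PROC MI (multiple imputations") will not bias the standard errors. This is worded as an expectation, not an instruction.
- **NMAR:** "if missing data are NMAR, we will use the 'pattern mixture' approach to compute a weighted average of the parameters" linked to the missing data, so as to estimate the values that were not seen.

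A general sentence adds: "Necessary transformation and imputations will be carried out based on the raw data distribution".

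For the primary comparison: "We will utilize both repeated-measures ANOVA and random mixed effect models to compare the trajectory change in graft function" and in the proportion of regulatory T cells. Then: "The method of estimation will be maximum likelihood (ML"). The plan does not say how imputed data and these models fit together. No section says how eGFR after graft loss or death is treated, whether it counts as missing, or in which class.

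**The concern.** A missed clinic visit hides an eGFR that exists. Graft failure means there is no graft function left to measure, and after death there is no eGFR at all. The plan puts all three under one heading. If the value after a failed graft is treated as missing at random, it is predicted from eGFR recorded while grafts were working. A patient who lost the graft then contributes preserved function to a primary endpoint, and the arm with more losses looks better than it was.

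The separate graft-loss analysis is weak protection. The Sample size and power section says power was not considered for the secondary endpoints and that a much larger trial would be needed for them. The trial is also open label, so a choice between branches made after the data are seen is a choice made with treatment known.

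**Working it through.** **1. The plan's own power figure.** The plan states power 0.82 for an effect size of 1.0 with 20 per arm, two-sided alpha 0.05 and 10% attrition. With n = 20 × (1 − 0.10) = 18 per arm, a two-sample t-test (noncentral t) gives 0.83. For effect size 2.0 the plan states 0.99, and the calculation gives more than 0.999. The stated power is reproduced. It fixes the yardstick of 1.0 SD for graft function but says nothing about missing data.

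**2. What each route does with eGFR after graft loss.**

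- *PROC MI (MCAR/MAR):* values are drawn from a model fitted to observed eGFR, which comes from working grafts.
- *ML mixed model without imputation:* under MAR, the fitted month-36 mean applies to all patients as if each had continued on a trajectory like the observed ones. The extrapolation is implicit but of the same kind.
- *Pattern mixture (NMAR):* the stated aim is still to estimate the unseen values. That has no clear meaning after death, and it does not by itself record a failed graft as lost function.
- *Choice of route:* no criterion is given. Observed data can give evidence against MCAR but cannot separate MAR from NMAR.

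**3. Size per graft loss.** The documents give no eGFR level, SD or number of losses, so every input here is assumed: predicted eGFR m = 45 to 65 mL/min, SD s = 15 to 20, n = 18 to 20 per arm, one loss in the arm. The comparison is between predicting m and counting no function (0).

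- Shift in the arm mean = m / n. Lowest: 45/20 = 2.25. Highest: 65/18 = 3.6 mL/min.
- Shift in SD units = m / (n × s). Lowest: 45/(20 × 20) = 0.11. Highest: 65/(18 × 15) = 0.24.

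A variant, also assumed, takes a mean of 50 to 60, a value of 0 to 10 for a lost graft, and 20 per arm. The lowest shift is (50 − 10)/20 = 2.0 and the highest is (60 − 0)/20 = 3.0 mL/min, or 0.10 to 0.20 SD. Two losses double this to 0.20 to 0.40 SD.

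**4. Price of scoring a loss as zero.** With one zero in an arm of 18, p = 1/18 and the variance is multiplied by (1 − p) + p(1 − p)(m/s)².

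- m/s = 45/20 = 2.25: 0.944 + 0.0525 × 5.06 = 1.21, so the SD rises by a factor of 1.10.
- m/s = 65/15 = 4.33: 0.944 + 0.0525 × 18.8 = 1.93, so the SD rises by a factor of 1.39.

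With one loss in each arm and an unchanged raw difference of 1.0 original SD, the effect size becomes 1/1.10 = 0.91 or 1/1.39 = 0.72. Power at 18 per arm falls from 0.83 to about 0.76 or 0.56.

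**The case against.** A reader might infer that multiple imputation is the plan's rule for all missing primary data, so that a failed graft is bound to receive an imputed working eGFR. The documents do not support that. PROC MI belongs to one conditional branch, and the next sentence sends NMAR data to pattern mixture, where eGFR absent because of graft failure could be classed. The primary model is fitted by maximum likelihood and can use incomplete records with no imputation. Filling in from working grafts is a possible outcome, not a prescribed one. This limits the point, but neither alternative removes it: the ML model extrapolates under MAR as well, and the pattern-mixture branch has no provision for these events.

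Other objections stand in part.

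- Recipients have living donors and PRA below 20%, and no event rate is given. Listing graft loss and death as endpoints does not show that they will be frequent. With no losses there is no effect.
- A prediction that uses a patient's own declining eGFR could fall below 45 to 65, which would shrink the shift.
- Graft losses are not hidden, since they are analysed separately.
- Calling the shift a bias presumes that a lost graft should count as lost function. That is a choice of estimand, and scoring zero has a real cost in precision. This argues for a companion analysis, not for zero-scoring as the sole primary analysis.

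**Conclusion.** The point holds as an unspecified rule with a predictable direction. The plan does not distinguish missed visits from eGFR that no longer exists, and both the MAR branch and the ML model, followed as written, predict function for lost grafts. For graft loss this favours the arm with more losses. For death with a working graft the direction is not clear, and the difficulty is one of meaning.

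On the assumed inputs each loss is worth 0.11 to 0.24 SD, at most about a quarter of the design effect. That is modest, it depends on losses occurring, and it matters only as far as they differ between arms. In arms of about 20, one or two losses could still change how a borderline result reads. The plan should be changed; the design is not undermined.

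**What to change.** In the Statistical analysis section:

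1. Define three cases: a missed visit with a functioning graft, eGFR after graft loss, and eGFR after death.
2. Limit PROC MI, and the MAR assumption in the mixed model, to the first case. Removing later visits from PROC MI alone is not enough, because the ML model would still extrapolate over them.
3. Do not impute eGFR after death; analyse it while the patient is alive.
4. Alongside the observed-value mixed model, pre-specify an analysis that counts graft loss as no function, either eGFR 0 or worst rank. Worst rank avoids inflating the SD.
5. State that the observed-value model rests on extrapolation after graft loss, and report any difference between the two analyses in the conclusion.
6. Set these rules in advance, in place of a classification of the mechanism from the trial data.

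The cost is a few sentences and one extra analysis. If losses occur, the zero-scored version is less precise: on the assumed figures the SD rises by about 10 to 39% with one loss per arm of 18.

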The present proposal is designed to investigate the mechanisms of the synergistic effect(s) of low dose CNI and mTOR inhibitors (Everolimus) in controlling alloreactive T and B cells while expanding Tregs.

Our hypothesis, based on published data and our laboratory results (see preliminary data-Supportive documents), is that mTOR inhibitors allow expansion of Tregs and that low exposure to CNI is sufficient to control alloreactive T cells. Decreased exposure to CNI and concomitant increase of Tregs will then translate to improved renal allograft function and histology.

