### **Sample size and power**

[figure not shown]
We calculated our sample power for the two primary endpoints based on our clinical experience and small pilot data. Using a two-tailed  $\alpha$  of 0.05, the anticipated effect sizes corresponding to each specific aim between the two treatment arms were calculated using a minimum of 80% statistical power and assumed 10% attrition at 12 months.

For the sample size of  $n= 20$  in each group, the proposed study will have a power of 0.82 and 0.99 to detect effect size of 1.0 and 2.0 for graft function and % regulatory T cell change, respectively, between the two treatment arms. Because this is a pilot study, we do not consider the statistical power of secondary outcomes; It is anticipated that a much larger sample size will be needed in order to achieve statistical power for the secondary endpoints in this proposed study.

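### The primary Treg hypothesis is about numbers, but the model and the power statement are about a proportion with no stated denominator

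*Combined protocol and SAP*

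**What the plan says.** The Combined protocol and SAP describes the Treg outcome in several places.

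- **Overall hypothesis** (Study purpose and rationale): "mTOR inhibitors allow expansion of Tregs and that low exposure to CNI is sufficient to control alloreactive T cells". No unit is attached to expansion.
- **Primary endpoint** (Statistical analysis): besides the function of the graft, it is "subpopulations of T cells, including regulatory T cells and B cell subpopulations at 3, 6, 12, 24 and 36 months post kidney transplant". Again no unit.
- **Primary hypothesis** (Statistical analysis): everolimus recipients will show "higher numbers of regulatory T cells as compared to the standard dose CNI+MMF group".
- **Primary model** (Statistical analysis, the next paragraph): repeated-measures ANOVA and mixed models will "compare the trajectory change in graft function and proportion of regulatory T cells over 12, 24 and 36 months".
- **Power** (Sample size and power): "power of 0.82 and 0.99 to detect effect size of 1.0 and 2.0 for graft function and % regulatory T cell change".
- **Phenotype** (Study design, treatment-arm text): "regulatory T cells (Treg: Foxp3+CD4+ CD25bright" and positive for CD25. Flow cytometry is the assay. Neither a denominator nor an absolute-count method is described.
- **Baseline** (Study design, treatment-arm text): blood is taken before randomization, and the follow-up samples are to be used to examine the "subpopulation of T cells in comparison with baseline levels". The Statistical analysis section enters baseline characteristics as covariates only where the two arms turn out to differ.

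**The concern.** The hypothesis names one variable and the model analyses another. A Treg percentage can rise because Tregs increase or because the other cells in the denominator decrease. The trial's scientific claim is expansion, which a higher percentage alone does not establish.

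Parent-cell counts could plausibly differ between these arms. All recipients receive the same Campath induction, but only the control arm receives MMF, and the MMF dose is adjusted when the white-cell count falls. If counts differ, a result on proportion could be reported as support for a statement about numbers that was never analysed.

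A second, smaller matter is that a baseline Treg value is available for every recipient sampled as planned, yet whether it enters the primary model depends on observed imbalance. That gives up precision that costs nothing to obtain.

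**Working it through.** **1. The plan's own power.** Inputs from Sample size and power: 20 per arm, 10% attrition at 12 months, two-sided alpha 0.05, effect sizes 1.0 and 2.0.

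Evaluable per arm: 20 × 0.90 = 18. For a two-sample t-test, the noncentrality is d × √(n/2), with 34 degrees of freedom.

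- d = 1.0: 1.0 × √9 = 3.0, power 0.830 (stated 0.82).
- d = 2.0: 2.0 × √9 = 6.0, power 0.9999 (stated 0.99).

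Both agree to within 0.01. Without attrition (n = 20) the first would be 0.869, so the stated figure evidently allows for dropout. The effect size is standardized and the readable text labels its Treg scale as a percentage. A figure in that section is not available to check.

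**2. How proportion and number part.** Number = proportion × parent-cell count, so number ratio = proportion ratio × count ratio. An illustration with assumed counts, since the documents give none:

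- Arm A: 8% of 200 cells/µL = 16 Tregs/µL.
- Arm B: 5% of 400 cells/µL = 20 Tregs/µL.

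The proportion ratio is 8/5 = 1.6, the count ratio 200/400 = 0.5, and the number ratio 1.6 × 0.5 = 0.8. With a proportion ratio of 1.6, the direction reverses once the count ratio falls below 1/1.6 = 0.625.

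**3. What the 0.99 implies for numbers.** No SD or effect for absolute numbers is given, so only a range under assumptions is possible. Assume a log scale, independent components, an effect of 2.0 SD on the log proportion, and 18 per arm. Let r be the SD of log parent count divided by the SD of log proportion, and s the between-arm shift in log parent count (everolimus minus control, in SDs of log count). Then

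d(number) = (2 + s × r) / √(1 + r²).

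| r | s = 0: d | power | s = −0.5: d | power |
|---|---|---|---|---|
| 0.5 | 1.79 | 0.999 | 1.57 | 0.995 |
| 1 | 1.41 | 0.985 | 1.06 | 0.871 |
| 2 | 0.89 | 0.741 | 0.45 | 0.256 |
| 3 | 0.63 | 0.454 | 0.16 | 0.075 |

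The shift could go the other way. With s = +0.5 and r = 2, d = (2 + 1)/√5 = 1.34 and power is 0.974.

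**4. Value of the baseline covariate.** With correlation ρ between the baseline and follow-up percentage, adjustment leaves a residual variance of 1 − ρ². The documents do not give ρ. Assumed values:

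- ρ = 0.3: 1 − 0.09 = 0.91
- ρ = 0.5: 1 − 0.25 = 0.75
- ρ = 0.7: 1 − 0.49 = 0.51

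The baseline sample precedes randomization and induction is given at surgery, so a low correlation is possible.

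**The case against.** The best defence is that numbers is loose wording. The Statistical analysis section elsewhere speaks of the frequency of cell subsets, the power statement uses a percentage, the assay is flow cytometry, and the supporting abstract reports percentages. On that reading the sponsor always meant Treg percentage, and one word is out of line. This may well be so, but the documents do not settle it. It also leaves the denominator unstated and the expansion claim resting on a percentage.

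The count illustration is also open to challenge. It uses invented counts and puts the lower count in the arm with the higher proportion. The only hint in the documents about counts concerns MMF in the control arm, which would point the other way if it pointed anywhere. That is fair. The illustration shows that divergence is possible; it does not predict its direction.

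Three stronger readings are tempting, and the documents support none of them.

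- **Three different Treg quantities are in play.** The power statement's "regulatory T cell change", preceded by a percent sign, could mean percent change from baseline. It reads more naturally as change in the percentage, which matches the modelled change in proportion. That leaves two quantities.
- **The baseline sample goes unused.** The Study design text plans a comparison with baseline, and covariates may enter if the arms differ. The plan lists no explicit model terms, so its silence is not an exclusion.
- **The false-positive rate is inflated by choosing a scale after seeing the data.** The primary Treg model names one variable, and nothing in the plan provides for testing several and selecting among them.

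**Conclusion.** The mismatch between hypothesis and analysis is real. If numbers means counts, the primary analysis does not test the primary Treg hypothesis. If it means percentage, the hypothesis is misworded and its denominator is missing. In either case a positive result would support a higher proportion, not higher numbers or expansion.

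No figure in the plan is wrong: the stated powers reproduce. They apply to the scale from which the effect size of 2.0 was taken, which the text labels as a percentage. For absolute numbers the plan offers no power, and the range of about 0.08 to above 0.99 depends entirely on the assumed count variability, between-arm shift and independence.

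On baseline, the supported statement is that no baseline Treg term is prespecified and that covariate adjustment depends on observed imbalance. With the Treg power already stated at 0.99, the gain is mainly a more precise estimate and a rule fixed in advance.

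**What to change.** 1. Reword the primary hypothesis as Treg percentage, state its denominator (the parent population by phenotype), and use the same term in the model and the power statement. Say explicitly that the powered quantity is change in that percentage, if that is what was meant.
2. Prespecify the pre-randomization Treg percentage as a covariate in the primary Treg model, whatever imbalance is observed. If the sponsor intends baseline to be one of the repeated responses instead, the plan should say so and not also enter it as a covariate.
3. Name absolute Treg number as a supportive outcome. Derive it as Treg percentage × parent-cell count, with the parent count obtained from the CBC and the parent fraction by flow cytometry, and state how the CBC is matched to the research blood draw.
4. Limit the conclusion to a higher proportion unless the absolute number also supports expansion.

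The cost is a wording change, a small derivation from tests already planned, and a narrower claim if the numbers do not follow the proportion. No additional recipients or visits are needed.
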